Baseline assessment. Staff will call and/or email participants within 3 days of their scheduled baseline assessment to remind them of the appointment. The baseline assessment will include informed consent measurement of height and weight, completion of a contact information sheet, and completion of additional measures which will be used to determine eligibility (screeners for depression and binge eating disorder). Study personnel will also help participants download My Fitness Pal app (all) and an app to track time on Facebook (Android users) and provide instruction of how to use these apps. For iPhone users, personnel will also show them how to locate Facebook app usage data using the battery settings. We expect the baseline study visit to take 30-45 minutes. Following the baseline assessment, research staff will fax the medical clearance form to participants' primary care provider or OBGYN. After the baseline visit, staff will email participants a link to complete a survey via REDCap. A copy of the baseline survey is enclosed. We will email participants a \$20 gift card after they have completed the baseline visit and online survey.

Orientation Webinar. Participants will complete a 60-minute orientation webinar. The purpose of the webinar is to educate participants about what research is, review study procedures, review importance of participation of enrolled participants, and to allow participants another opportunity to evaluate if joining this study is the right choice for them. This webinar is being conducted to improve study retention. The webinar moderator will record in REDCap tracking which participants completed the webinar.

Pre-Randomization Survey. Following the orientation webinar, we will email participants a short online survey that includes Facebook time measures and completion of a randomization agreement. We will email participants a copy of the randomization agreement form for their records. A copy of the pre-randomization survey is enclosed.

Participants will need to complete the telephone screening, baseline assessments (visit and survey), and orientation webinar, and pre-randomization survey before being randomized.

Randomization. We will randomize participants 1:1 to the FB and IP conditions in randomly permuted blocks of size 4 and 6. Randomization will be stratified by weeks post-partum at enrollment (8 weeks to <6 months, 6-12 months) and smartphone type (iPhone vs Android) .

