6-month follow-up assessment. At 6 months, women will participate in an in-person focus group session. We will email participants a link to complete an online survey before this visit. The survey will be administered via REDCap. Research staff will measure participants' weight individually as women are arriving for the focus group. We will ask participants in both treatment conditions to elaborate on what motivated or hindered participation. Focus groups with women in the Facebook condition will explore their reactions to and ratings of the format of low or high engagement posts (same procedures as the pre-trial focus group in Phase 1). For participants unable to attend the focus group session, we will schedule individual follow-up assessments and will conduct an individual interview (in-person or via phone) following the content of the focus group guide. We will audiotape the focus group and individual interviews. When scheduling the 6-month assessment, we will remind participants that we will audiotape the focus groups. For participants who are not comfortable with this discussion being audiotaped, we will schedule an individual visit and take notes during the interview. For follow-up assessments (both 6-month and 12-month), participants who are not willing to attend an in-person visit will be asked to self-report their current weight, and those who do not complete the survey online will be offered the option of completing the survey via phone. We expect that this study visit will take 1-1.5 hours and the survey will take 30-45 minutes. We will email participants a \$40 gift card after they complete the study visit and survey.

Due to weather or to prevent spread of illness (e.g., coronavirus), we may hold the focus group discussions via video or telephone conference call. In this case, participants would complete ratings of intervention posts via online survey. In the case of remote focus groups, we would ask participants to self-report their weight and not require in-person visits.

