12-month follow-up assessment. 12-month individual follow-up visits will include measurement of weight. Research staff will provide participants with instructions on how to remove the My Fitness Pal and time-tracking apps from their phones, and will assist participants with removal of these apps if desired. We will email participants a link to complete the survey at home following the 12-month follow-up study visit. The survey will be administered via REDCap. We expect that the survey will take about 30 minutes, and the visit will take about 15-45 minutes. We will email participants a \$40 gift card after they complete the study visit and survey.

Due to weather or to prevent spread of illness (e.g., coronavirus), we may participants to self-report their weight and not require in-person visits.

For all study assessments, research staff will call subjects who do not attend their scheduled in-person study visit to reschedule. Calls will follow the same calling procedures as the eligibility screen (see Eligibility Screen). We will reschedule the study visit a maximum of 5 times, with a maximum of 5 calls per scheduled visit before considering the woman lost to follow-up. Women who do not complete the online surveys will be sent two reminder emails containing a personalized link, at least 24 hours apart. After 7 days, research staff will may participants who have not completed the measures online to provide the participant the option of completing any remaining measures over the phone. Calls will follow the same calling procedures as the eligibility screen (see Eligibility Screen).

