- Recruitment. Recruitment rates will be calculated from the number of patients approached and reasons for ineligibility and non-participation. We will report numbers and reasons for recruitment using a CONSORT diagram.^{46,47}
- Sustained participation. We will calculate sustained participation as time to last intervention session attended in the IP condition and as time to last post, comment, or reaction (based on date of last post or comment reacted to) in the Facebook condition. In the Facebook condition, we will also calculate a secondary measure of sustained participation that includes last report of lurking.²⁵
- Contamination. We will describe the proportion of participant in both treatment conditions who report participating in other weight loss programs (online or in-person), seeking weight loss support on Facebook or other online social networks⁴⁴ at 6 months. We will also describe the extent of contamination and reasons women sought these extra sources of support using survey data and qualitative data from post-intervention focus groups.
- Retention. We will calculate retention as the proportion of participants who complete the 6- and 12-month follow-up study visits in each condition and report this information using a CONSORT diagram^{46,47}
- Feasibility of assessment procedures. We will examine the extent and mechanisms of missing data on each measure to be included in the subsequent non-inferiority trial.
- Weight loss. We will calculate percent weight change at 6 and 12 months by subtracting baseline weight from follow-up weights. We will define clinically significant weight loss as $\geq 5\%$.^{29,30}

Aim 2: Intervention refinement. In post-intervention focus groups, we will solicit women's feedback on posts with low engagement, and will iteratively refine these posts to make them more engaging. We will

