Aim 3: Measuring time on Facebook. We will compare self-reported time spent on Facebook to participate in the intervention with application-tracked time on Facebook, changes in use, and time spent visibly engaging, to develop procedures for measuring time that balance accuracy and participant burden. We will compare self-reported time spent on Facebook to participate in the intervention with (1) application-tracked time spent on Facebook, (2) change in application-tracked time over the intervention, and (3) estimated time spent visibly engaging in the intervention using paired t-tests and Wilcoxon rank-sum tests, as appropriate. We will also examine accuracy in reporting total time on Facebook at baseline and adjust self-reported time spent on Facebook to participate in the intervention accordingly. From these comparisons, we will develop procedures for measuring time spent on Facebook to participate in the intervention that maximize accuracy while not placing undue burden on participants nor changing their behavior as a result of surveilling their social media activities.

Inclusion/Exclusion Criteria: [List ALL inclusion and exclusion criteria. Any proposed exclusion criterion based on gender (women of childbearing potential), age, or race must include justification for the exclusion. Describe the conditions under which participants may be removed from the study, i.e., noncompliance with study rules, study termination, etc.]

Only women will be included as the aim of this study is to refine a post-partum weight loss intervention.

Inclusion criteria. Women aged ≥ 18 years, 8 weeks to 12 months post-partum at enrollment, overweight or obese ($BMI \geq 25$ kg/m²) per measured height and weight at the baseline visit, owns a scale (we will provide women with a scale if needed), comfortable reading and speaking English, owns an iPhone or Android smartphone, active Facebook user as defined as daily Facebook use and posts/comments at least weekly over the past 4 weeks, clearance from primary care provider or obstetrician/gynecologist, willing and able to participate in either treatment condition (Facebook or in-person), available to attend in-person meetings over the 6-month study period in Hartford, CT, 45 minutes or less to travel to intervention meetings, and willing and able to provide informed consent.

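### Does the plan need a rule for combining staff-measured and self-reported follow-up weights in the percent weight loss result?

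*Protocol*

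**What the plan says.** Under Baseline assessment the protocol states: "The baseline assessment will include informed consent measurement of height and weight". The inclusion criteria define overweight and obesity "per measured height and weight at the baseline visit", so the baseline value is a measured one.

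At 6 months staff weigh women as they arrive for the focus group, and the 12-month visit includes a weight measurement. There are exceptions. At both follow-ups, "participants who are not willing to attend an in-person visit will be asked to self-report their current weight". For weather or illness, the 6-month section adds: "In the case of remote focus groups, we would ask participants to self-report their weight and not require in-person visits". The 12-month section has a matching provision, with a word evidently dropped: "we may participants to self-report their weight and not require in-person visits".

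The analysis text (Data Analysis, Aim 1, Weight loss) is: "We will calculate percent weight change at 6 and 12 months by subtracting baseline weight from follow-up weights". It sets clinically significant loss at 5% or more. The SAP section Weight loss (exploratory) promises percent loss at each time point by condition. Neither text mentions the source of a weight. The SAP's opening section calls weight change exploratory and its reporting descriptive.

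**The concern.** With baseline always measured and follow-up sometimes self-reported, a systematic gap between the two methods does not cancel within a woman. It passes into the mean percent loss and into the share reaching 5%.

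The two arms would be affected alike only if both the proportion self-reporting and the size of the error were alike. Willingness to attend could differ between a Facebook arm and an in-person arm. Remote follow-up could also cover a whole wave, which is 36 of the 72 women.

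The missing-data review may not reveal any of this, because a self-reported weight need not be counted as missing. A reader of the results might then be unable to tell how many follow-up weights were measured.

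**Working it through.** **1. Is there a stated figure to reproduce?** No. The protocol gives no precision, power or margin for weight. Its only precision figure concerns retention and does not bear on this point.

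**2. What do the passages imply together?** The follow-up sections make self-report the replacement when a visit does not take place. The analysis section then uses follow-up weights with no restriction. Read together, all available follow-up weights enter the percentage. What is absent is an explicit statement of this and a promised breakdown by source.

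**3. How large could the effect be?**

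*From the protocol:* SD of percent loss 4.2 and mean 4.8 (one-arm pilot); 36 women per condition; 80% retention regarded as acceptable, which gives 36 × 0.8 = 28.8 per arm.

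*Assumed, not in the documents:* baseline weight 85 kg; reporting error b of 0.5 to 1.5 kg in either direction; a fraction f of the arm self-reporting.

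Shift per self-reporting woman, d = 100 × b / 85: 0.59, 1.18 and 1.76 points for b = 0.5, 1.0 and 1.5 kg.

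Shift in the arm mean = f × d. For the share at 5% or more, a normal model with mean 4.8 and SD 4.2 gives 48.1% with no error, and a fraction f of the arm is moved by d.

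| f | Shift in mean (points) | Shift in 5% share (points) |
|---|---|---|
| 0.25 | 0.15 to 0.44 | 1.4 to 4.1 |
| 0.50 | 0.29 to 0.88 | 2.8 to 8.2 |

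With no reporting error every entry is zero. The normal model is rough: the pilot itself observed 58% at or above 5%.

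Sampling error for comparison:

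| | 36 per arm | 28.8 per arm |
|---|---|---|
| SE of mean, 4.2/√n | 0.70 | 0.78 |
| SE of share, √(0.481 × 0.519/n) | 8.3 points | 9.3 points |
| SE of arm difference in means, 4.2 × √(2/n) | 0.99 | 1.11 |

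The fraction at which the mean shift equals one standard error is SE/d:

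- At 1.5 kg: 0.70/1.76 = 40% with 36 per arm, or 0.78/1.76 = 44% with 28.8.
- At 1.0 kg: 0.70/1.18 = 60%, or 0.78/1.18 = 67%.
- At 0.5 kg it cannot be reached, since 0.70/0.59 exceeds 1.

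These depend on the assumed baseline. For 1.5 kg and 36 per arm, d is 2.0 at 75 kg and 1.5 at 100 kg, so the fraction runs from 0.70/2.0 = 35% to 0.70/1.5 = 47%.

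Between arms:

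- Half self-reporting in both arms, with errors of 1.0 and 0.5 kg: 0.5 × 100 × 0.5/85 = 0.29 points.
- Equal error, with 10% self-reporting in one arm and 40% in the other: 0.30 × d = 0.18 to 0.53 points.

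Both are below the 0.99 standard error of an arm difference.

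**4. Would a measured-only analysis settle it?** Suppose half of the 28.8 women per arm are measured, that is 14.4. The standard error of the measured-only mean is 4.2/√14.4 = 1.11. The standard error of the difference between the all-weights mean and the measured-only mean is 4.2 × √(1/14.4 − 1/28.8) = 0.78 points. The largest shift in the half-self-report case is 0.88, so the comparison could barely detect even that. Women who attend may also differ from those who do not. If one wave were followed remotely, source would be confounded with wave as well.

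**The case for a change.** The best argument for a change is that this pilot exists to prepare a non-inferiority trial whose hypothesis concerns weight loss, and that feasibility of assessment procedures is among the SAP's primary outcomes. How often weight could be measured by staff, in each arm, is useful for that purpose. Aim 3 already checks self-reported Facebook time against tracked time, while weight has no parallel check. The cost would be one sentence, one variable and a small table.

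It is right that the documents contain no rule on source and that a count by arm and visit would be informative. The rest is weaker:

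- The protocol says: "We will examine the extent and mechanisms of missing data on each measure to be included in the subsequent non-inferiority trial". If staff-measured weight is such a measure, each self-report counts as a missing measurement and would appear there. If retention counts only in-person visits, comparing it with the number of weights would also show non-attenders. Neither reading is certain, but the gap may be smaller than it looks.
- Illness-driven remote follow-up would ordinarily reach both arms of a wave, which weakens the concern about imbalance.
- Staff may reschedule a visit up to five times before a woman is treated as lost, which favours measured weights. Every participant owns or is given a scale, which may keep reporting error small.
- The enclosed surveys and grant application are not available here and may already deal with source.

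**Conclusion.** No change to the plan follows. This is missing detail that analysts would fill sensibly: include all follow-up weights, as the text implies, and state how many were measured and how many self-reported in each condition at each visit. A measured-only summary could sit beside this as description, but it cannot isolate reporting error.

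No stated rule produces a wrong result. The protocol's one numerical feasibility threshold is retention below 60%, and weight does not enter it. On the assumptions above, the shift in an arm mean stays within one standard error unless self-report is both common and considerably in error, roughly 40% or more of an arm at 1.5 kg. The documents support no particular value for the self-report fraction or for the size or direction of the error, which may be zero.

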Design, Procedures, Materials and Methods: [Describe the study design, including the sequence and timing of all study procedures. Experimental procedures should be clearly described and labeled as such. If the study uses control or experimental groups, or different treatment arms, clearly describe what participation will be like for each of the groups or study arms. Tip: describe procedures in the order conducted. The IRB strongly suggests that investigators incorporate *flexibility* into the study design to accommodate anticipated events (i.e. explain how missed study appointments can be made up by participants). If the research involves study of *existing samples/records*, describe how authorization to access samples/records will be obtained. If the study involves use of *deception* explain the reason why this is necessary. If applicable, describe the use of audiotape and/or videotape and provide justification for use. If this study offers treatment for the participants’ condition, complete the Treatment Study Supplemental Form (IRB-1C) and attach it to this application for review. If the study includes *measures, survey instruments and questionnaires*, identify each and, if available, provide references for the measures. Describe what they intend to measure (relate to purpose/hypothesis) and their psychometric properties (e.g., reliability and validity). Identify any that were specifically created for the study.]

Participation will include a baseline assessment, an orientation webinar, participation in a 6-month weight loss intervention, and follow-up assessments at 6 and 12 months. Study visits and in-person treatment sessions will take place in a private space (such as a conference room, exam room, or classroom) at UConn Storrs, UConn Hartford, the Hartford Public Library, Hartford Hospital, Women’s Ambulatory Health Services, or WIC offices. Overall, it is estimated that completing study assessments will take approximately 5-6 hours and participating in treatment sessions (in-person condition) or engaging with

the counselor and other participants online (Facebook condition) will take approximately 90 minutes per week over the 6-month intervention period.

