Study title: The Healthy Moms Study: Comparison of a Post-Partum Weight Loss Intervention
Delivered Via Facebook or In-Person Groups

NCT 03700736

Statistical Analysis Plan

Date of document: 10/20/2021

Statistical Analysis

We will use Research Electronic Data Capture (REDCap) to administer participant surveys and for participant tracking and data management. We will use SAS 9.4 (SAS Institute, Inc., Cary, NC) to analyze quantitative data. Reporting of the feasibility outcomes and exploratory outcome of weight change will be descriptive (e.g., percent retention at 6 and 12 months).

Primary Outcomes: Feasibility

Examination of feasibility outcomes will inform the design of the subsequent full-scale non-inferiority trial.

Recruitment. We will report recruitment using a CONSORT diagram. We will compare yield from different recruitment approaches, and will examine whether any eligibility criteria are excluding an inordinate proportion of otherwise eligible women. In particular, we will examine the number of otherwise-eligible women excluded from participation because one or the other delivery mode is not feasible or unwillingness to be randomized to either treatment condition. If recruitment rates are lower than expected, we will adjust recruitment timelines as we plan the subsequent non-inferiority trial.

Sustained participation. We will report sustained participation in both conditions. We will modify the delivery of both intervention conditions to address logistical and other barriers to sustained participation.

Contamination. We will report the extent of contamination and reasons women sought these extra sources of support. If a significant proportion of women report seeking weight loss support from other sources, we will adapt our intervention to better meet their needs to reduce the occurrence of contamination in the subsequent trial.

Retention. We will report retention in each condition. If retention is lower than expected, we will explore reasons for drop-out and make changes to the protocol to address these challenges. We will also report the proportion of participants who become pregnant within the study period.

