Feasibility of assessment procedures. We will examine the extent and mechanisms of missing data, particularly measures of costs associated with delivering and receiving the intervention. For measures with an unacceptable amount of missingness, we will consider alternate measures in the subsequent non-inferiority trial. We will resolve any issues arising in the collection of data needed for the cost-effectiveness aim of the subsequent efficacy trial and develop procedures for assessing time spent on Facebook to participate in the intervention.

Weight loss (exploratory)

We will report percent weight loss at 6 months and 12 months in each treatment condition.

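### Aim 3's test of self-reported intervention time against total tracked Facebook time cannot show whether self-report is accurate, and the test against change in tracked time can do so only if ordinary use stays constant

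*Protocol*

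**What the plan says.** In the Protocol, Data Analysis, Aim 3, the quantity of interest is the time a woman reports spending on Facebook to take part in the intervention. It is set against three quantities:

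- (1) total tracked time: "We will compare self-reported time spent on Facebook to participate in the intervention with (1) application-tracked time spent on Facebook";
- the movement in that total, listed as item (2) and worded as "change in application-tracked time over the intervention";
- (3) estimated time visibly engaging in the intervention.

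The comparisons are to be made "using paired t-tests and Wilcoxon rank-sum tests, as appropriate". The next sentence adds a separate check, "We will also examine accuracy in reporting total time on Facebook at baseline", and says self-reported intervention time will be adjusted accordingly. The stated purpose is to develop a measurement procedure that balances accuracy and burden.

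The Baseline assessment section describes the tracking: an app that records time on Facebook for Android users, and the Facebook app's usage data in the battery settings for iPhone users. Neither is described as separating the study group from the rest of Facebook. The inclusion criteria require an "active Facebook user as defined as daily Facebook use and posts/comments at least weekly over the past 4 weeks".

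The SAP says "Reporting of the feasibility outcomes and exploratory outcome of weight change will be descriptive". Under feasibility of assessment procedures it says the team will "develop procedures for assessing time spent on Facebook to participate in the intervention", next to the data needed for the later trial's cost-effectiveness aim. It neither repeats nor withdraws the Aim 3 tests.

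**The concern.** A test of mean difference tells us about the accuracy of a report only if the comparator measures the same thing. Comparator (1) does not. It contains all of a woman's ordinary Facebook use as well as her time in the study group, so the null hypothesis of no difference is false by construction for women who take part by phone. A woman who over-reports moves closer to the tracked figure until her report reaches the total.

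Comparator (2) subtracts ordinary use, but only the part that stays the same. If ordinary use drifts over six months, or if time in the group replaces other Facebook time, the change no longer equals intervention time. Accurate reports can then look wrong, or wrong reports look accurate.

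Aim 3 exists to choose how intervention time will be measured, and the SAP ties that choice to later cost data. The Protocol says the procedures will be developed from these comparisons, but not how (1) and (2) are to be read.

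**Working it through.** The plan gives no sample size, alpha or effect size for Aim 3, so there is no figure to reproduce. The rejection rates below only illustrate the logic.

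**Inputs from the Protocol**
- Ordinary use: 50 min/day (Background, a figure for Facebook users in general), so 50 × 7 = 350 min/week.
- Intervention time: participation "will take approximately 90 minutes per week over the 6-month intervention period" (Design section), so 90 min/week.
- n = 36 per condition. At the 80% retention considered in the sample-size section, 0.8 × 36 = 28.8, or about 29.

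**Assumptions not in the documents:** all SDs, drift and substitution. Tests are two-sided paired t-tests at 5%, with power from the noncentral t distribution (noncentrality = gap × √n / SD).

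**Comparison (1).** Gap = ordinary use + 90 − report.

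| True 90; report is | Gap, ordinary use 350 | Rejection, SD 350, n=36 | n=29 |
|---|---|---|---|
| 45 (half) | 395 | over 99.9% | over 99.9% |
| 90 (exact) | 350 | over 99.9% | 99.9% |
| 180 (double) | 260 | 99.1% | 97.1% |

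The result is nearly the same whichever way women report. If group time fully replaces ordinary use, tracked time is 350 and the gap for an exact report is 350 − 90 = 260, which again gives 99.1% at n=36. A separate simulation (SD of total time 175 or 350; substitution of 0, 50 or 100%; reports exact, 50% low or 50% high) rejected in at least 99.8% of runs in every scenario tried.

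If ordinary use is half as large (175), the gaps are 220, 175 and 85. At n=36:
- SD 350: rejection 96%, 83% and 29%;
- SD scaled down to 175: about 100%, 100% and 81%.

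In both cases doubled reporting is rejected least often. The ordering follows from the design; its size depends on the assumed SD.

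**Comparison (2).** Gap = 90 + drift − substitution − report. Drift of 35 is 10% of 350; substitution of 22.5 is 25% of 90. Rejection at n=36:

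| Scenario | Gap | SD 60 | SD 100 | SD 150 |
|---|---|---|---|---|
| Half reported, ordinary use constant | 45 | 99% | 75% | 42% |
| Exact report, drift +35 | 35 | 93% | 53% | 28% |
| Exact report, drift +35, substitution 22.5 | 12.5 | 23% | 11% | 8% |
| Exact report, drift −35, substitution 22.5 | −57.5 | over 99% | 92% | 61% |
| Half reported, drift −35 | 10 | 16% | 9% | 7% |

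Row 1 shows that (2) works as a test of mean bias when ordinary use is constant. An exact report then has a gap of zero and is rejected at the nominal 5%. Rows 2 to 4 show false rejection of exact reports, and row 5 shows real misreporting being missed.

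These rates are sensitive to the SD. If weekly totals have SD 350 and correlate 0.7 over time, the SD of change is 350 × √(2 × 0.3) ≈ 271. Row 2 then falls to 12%, row 4 to 24% and row 1 to 16%.

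**Comparison (3) and the baseline check.** Visible engagement is specific to the intervention. It leaves out passive reading, which the Protocol recognises as lurking under Sustained participation, so it is a lower bound. The baseline check compares like with like, but for total time before the intervention starts. It cannot separate intervention time from other use later.

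**The case against.** The strongest reply is that Aim 3 does not set out to validate self-report against (1) or (2). Its purpose is to develop a procedure, and the Protocol nowhere says a difference will be read as misreporting. It plans four pieces of evidence: a total, a change, visible engagement, and a baseline accuracy check with adjustment. The total and visible engagement already bracket the truth for phone use. The SAP describes feasibility reporting as descriptive.

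Much of this stands, and it limits the harm. It does not rescue the test on (1): the Protocol names hypothesis tests, the SAP does not withdraw them, and neither document says what a significant or non-significant result on (1) would mean.

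A reader might go further and infer that neither (1) nor (2) can inform accuracy. The documents do not support that for (2). It targets intervention time directly when ordinary use is constant, and can then detect mean misreporting, as row 1 shows. A reader might also infer that Aim 3 as a whole cannot be answered. That does not follow either, because (3) and the baseline check do not depend on (1) or (2).

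It is also fair to say that the rejection rates rest on SDs, drift and substitution that come from outside the documents. The weekly and follow-up surveys were enclosed with the application but are not shown, so silence on exactly what they record is not a gap in the plan.

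**Conclusion.** The point holds in limited form and is minor. Comparison (1) is a part-whole comparison and cannot show whether self-reported intervention time is accurate. This rests on the tracker's scope and the daily-use criterion, not on any assumed SD. It applies to phone use; the documents do not say how use on other devices is counted. Comparison (2) is a usable test of mean bias under an unstated assumption of constant ordinary use. How far it could mislead cannot be fixed from the documents: false rejection of exact reports under the assumed drift and substitution ranged from 8% to over 99% for change SDs of 60 to 150.

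What is at stake is the reading of two comparisons in a pilot, one of which needs only a stated assumption.

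**What to change.** Amend the Aim 3 analysis text as follows.

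1. Do not test (1) as an accuracy comparison. Report it descriptively as an upper bound on intervention time for phone use, with (3) as a lower bound.
2. Extend the planned check of self-reported against tracked total time from baseline to follow-up weeks where both are recorded. Report the mean difference and its spread, not only a p-value.
3. Keep (2), and state that it equals intervention time only if ordinary Facebook use neither drifts nor is replaced by group time.
4. Add one sentence saying how (1) to (3) will be read together when the measurement procedure is chosen.

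The cost is a few sentences. No new data collection is needed, because item 2 applies only where both values already exist. A contrast of tracked time between the Facebook and in-person conditions could be added, but it is not needed. It would give a group mean rather than each woman's time, would not remove substitution, and would be imprecise: 1.96 × √(2 × SD² / 36) is about ±28 to ±69 min/week for assumed SDs of 60 to 150.
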